6.3 Power and Sample Size

We will have a power of 80%, as described in 10.1.1, with a sample size of 36 patients in each arm for a total of 72 patients, plus 8 patients to allow for attrition, for a total of 80 patients.

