4.2 Secondary Outcomes

- 4.2.1 Mean VAS-NRS pain score at 48 hours.
 - 4.2.1.1 For patients undergoing ISB with liposomal bupivacaine, the mean VAS pain score at 48 hours was 3.39 with a standard error of 0.37.¹⁰
 - 4.2.1.2 There are no existing data to predict the mean VAS pain score at 48 hours for patients undergoing ISB with plain bupivacaine + adjuvants, however a similar study using plain bupivacaine alone demonstrated a mean NRS (similar to VAS) pain score of 5.5 with standard error +/-0.5⁶. We expect the mean pain score to be slightly below this value, approximately 4.5.
- 4.2.2 Postoperative opioid consumption
 - 4.2.2.1 The mean rescue opioid consumption (in IV morphine equivalents) in the first 48 hours after receiving ISB using liposomal bupivacaine was 12.0 +/- 2.3 in a previous study.¹⁰
 - 4.2.2.2 We expect the patients treated with plain bupivacaine and adjuvants to use a similar average of 12.0 intravenous morphine equivalents in the first 48-hours following surgery. For the purpose of this study, we will convert IV morphine equivalents to oral codeine equivalents.
- 4.2.3 Satisfaction with surgical experience
 - 4.2.3.1 At the 48 hour mark, the patient's satisfaction with the surgical experience, satisfaction with pain control, and willingness to recommend the procedure to another patient will be assessed via Likert scale. Adverse events will also be evaluated.

Single Injection interscalene brachial plexus nerve block with adjuvants vs. Liposomal bupivacaine interscalene brachial plexus nerve block for total shoulder arthroplasty

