6.1 Analysis of Primary Objective

6.1.1 The VAS-NRS scale is an 11-point scale that assesses pain from 0- “No pain” to 10- “Worst possible pain”. For this study, a difference of ≥ 2 points will be considered to be clinically significant. Pain scores will be taken measured on departure from the PACU and at each 12-hour interval, and average pain scores for each cohort will be calculated. The area under the curve (AUC) for each cohort will be calculated using the least squares method. The inferiority threshold will be set as ≥ 2 points over 48 hours, which would result in an AUC difference of 96 point-hours.

Prior studies have found an AUC48 for ISB using liposomal bupivacaine to be 136.4 with a standard error of 12.09.¹⁰ There are no data evaluating the AUC48 for ISB using plain bupivacaine with adjuvants; however we estimate that the

Single Injection interscalene brachial plexus nerve block with adjuvants vs. Liposomal bupivacaine interscalene brachial plexus nerve block for total shoulder arthroplasty

pain scores will be within 20% of that of liposomal bupivacaine, resulting in an AUC48 of 163.0 or below, and a similar standard error of 12.09.

With a 2-sample t test using $\alpha = 0.05$ and $\beta = 0.1$, the study will be powered to detect a difference of 96 point-hours between the 2 groups with 36 subjects per arm.

To test for differences in these AUC between the 2 arms, an independent t-test will be used; if the observed p-value is <0.05 , statistical significance will be assumed. Two-sided t-test will be performed for statistical analysis once data collection is complete.

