6.2 Analysis of Secondary Objectives

- 6.2.1 For the mean VAS-NRS score at 48 hours, prior studies have found an average score of 3.8 with a standard deviation of 2.88 (standard error of 0.36) for ISB using liposomal bupivacaine.¹⁰ There have been no studies to evaluate the pain scores after ISB using plain bupivacaine with adjuvants. This study will be powered to detect a difference of at least 0.4 on the VAS-NRS scale. We will define the threshold for inferiority as a difference of ≥ 2 points on the VAS scale. Analysis will be conducted using a two-sample t test with $\alpha = 0.05$ and $\beta = 0.1$.
- 6.2.2 For the comparison of post-operative opioid consumption, each patient's total post-operative opioid usage during the first 48 hours will be converted to oxycodone equivalents. The geometric mean opioid consumption for each cohort will be calculated, and the two cohorts will be compared for statistical difference using a two-sample t test, with $\alpha = 0.05$ and $\beta = 0.1$.
- 6.2.3 Patient satisfaction will be assessed on POD#2 by 5-point Likert rating scale, and via a binary question of "would you recommend this pain relief regimen to the next patient". The results of these questions will be compared with a Fisher's Exact Test, with $\alpha = 0.05$.

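### Sections 6.1 and 6.3 give 90% and 80% power for the same 36 per arm, neither can be checked without an AUC SD, and the primary decision rule never uses the 96 point-hour margin

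*Combined protocol and SAP*

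**What the plan says.** On power, section 6.1 specifies a two-sample t test with alpha 0.05 and beta 0.1, and says that "the study will be powered to detect a difference of 96 point-hours between the 2 groups with 36 subjects per arm". Section 6.3 says "We will have a power of 80%, as described in 10.1.1, with a sample size of 36 patients in each arm". It adds 8 patients for attrition, for 80 in total. The numbered sections of the protocol end at 8.0.

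On variability, section 6.1 quotes an AUC48 of 136.4 with a standard error of 12.09 for liposomal bupivacaine (LB). It expects plain bupivacaine with adjuvants (PBA) to be within 20% of this, "resulting in an AUC48 of 163.0 or below, and a similar standard error of 12.09". No AUC SD and no source n are given. For the 48-hour pain score, section 6.2 cites the same source (reference 10) for "an average score of 3.8 with a standard deviation of 2.88 (standard error of 0.36", while section 4.2 cites it for "the mean VAS pain score at 48 hours was 3.39 with a standard error of 0.37".

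On the aim and the test, section 1.0 gives the purpose as showing non-inferiority. Section 6.1 sets an inferiority threshold of 2 points over 48 hours, "which would result in an AUC difference of 96 point-hours". The analysis is then described as follows: "To test for differences in these AUC between the 2 arms, an independent t-test will be used", with p < 0.05 taken as significance, and "Two-sided t-test will be performed for statistical analysis once data collection is complete".

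**The concern.** Two planned powers for one sample size mean that a reader cannot tell what 36 per arm was meant to deliver. With only a standard error for the AUC, and no sidedness given for the sample-size calculation, the reader cannot settle the matter by recalculating.

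The second part matters more for the conclusion. A margin is set, but the analysis text never compares anything with it. A two-sided test for a difference asks whether the difference is distinguishable from zero. Non-inferiority asks whether a difference as large as 96 in the wrong direction can be ruled out. These questions can have different answers on the same data, and the plan does not say which one decides the trial.

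**Working it through.** **Inputs.** Margin, which is also the difference to detect: 2 points × 48 h = 96 point-hours (6.1). Arms: 36 each (6.1, 6.3). Final test: two-sided, alpha 0.05 (6.1). AUC SE: 12.09 (4.1, 6.1). Largest expected true difference: 163.0 − 136.4 = 26.6 (6.1).

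**Method.** Noncentral t with 70 degrees of freedom. SE of the difference = SD × √(2/36) = 0.2357 × SD. Noncentrality = (difference to be resolved) / (0.2357 × SD).

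**1. Attempt to reproduce the plan's figures.** The attrition arithmetic reproduces: 36 + 36 = 72, and 72 + 8 = 80. The 36 itself does not, because no SD is stated. Solving backwards at two-sided 0.05 for a difference of 96:

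| Power | SD needed for 36 per arm | Source n implied by SE 12.09 |
|---|---|---|
| 90% | 123.9 | (123.9/12.09)² = 105 |
| 80% | 143.4 | (143.4/12.09)² = 141 |

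Neither SD nor either n appears in the plan.

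**2. Size of the contradiction, whichever figure is right.** If 36 per arm gives 90% (SD 123.9), 80% needs only 28 per arm. If 36 gives 80% (SD 143.4), 90% needs 48.

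**3. The one indirect route to an SD (assumption).** From 6.2, (2.88/0.36)² = 64. If the AUC standard error rests on the same 64 patients, SD = 12.09 × √64 = 96.7. Noncentrality is 96/(0.2357 × 96.7) = 4.21, and power at two-sided 0.05 is 98.6%. With the SE of 0.37 from 4.2 instead, n = (2.88/0.37)² = 60.6, SD = 94.1 and power is 98.9%. Neither matches 80% or 90%.

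**4. Link to non-inferiority.** For a non-inferiority test with margin 96, the distance to be resolved is 96 minus the true difference. At a true difference of zero this is 96, so one-sided 0.025 non-inferiority power equals two-sided 0.05 power for 96. At 26.6 the distance is 96 − 26.6 = 69.4:

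| SD | Power, true difference 0 | Power, true difference 26.6 |
|---|---|---|
| 96.7 | 98.6% | 85.1% |
| 123.9 | 90% | 65% |
| 143.4 | 80% | 53% |

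(one-sided 0.025, 36 per arm.) Power falls below 80% once the SD exceeds 143.4 at zero difference, or 103.6 at 26.6.

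**5. Can significance and non-inferiority disagree?** The 95% CI half-width is 1.994 × 0.2357 × SD.

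- SD 96.7: half-width 45.5. An observed difference (PBA minus LB) of 48 gives 2.5 to 93.5, which is significant and yet wholly below 96.
- SD 143.4: half-width 67.4. An observed difference of 50 gives −17.4 to 117.4, which is not significant and yet does not exclude 96.

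The second kind of disagreement needs a half-width above 48, that is an SD above 48/(1.994 × 0.2357) = 102.1.

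**The case against.** The strongest defence is that 96 is both the difference to detect and the inferiority threshold. The stated power can then be read as non-inferiority power at one-sided 0.025 with zero true difference. This stands. A reader might infer that the power statement has nothing to do with non-inferiority, and that goes too far. What remains is that the plan does not state a zero true difference, and its own planning limit is 26.6.

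A non-inferiority origin for 36 also cannot be excluded. With margin 96, true difference 26.6, SD 96.7 and one-sided 0.05, 34 per arm are needed for 90%, and 36 give 91.5%. But that calculation is not documented, its SD is borrowed, and its alpha does not correspond to the stated two-sided test.

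A reader might further infer that the sponsor will take a non-significant p-value as proof of non-inferiority. Section 6.1 does not say so; it says only that p < 0.05 will count as significant. The supportable point is narrower: the threshold is set but never tied to a confidence limit.

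Finally, one could say that the conflict is clerical and changes no procedure. That is fair for the power figures and the dead cross-reference taken alone, but not for the missing decision rule.

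**Conclusion.** The concern holds in this form. The conflict between 90% and 80% for 36 per arm is certain and rests on no assumption. So is the absence of section 10.1.1, of an AUC SD and of a source n. In sample-size terms, the gap is 28 against 36 per arm, or 36 against 48. The gap in the decision rule is also plain from the text: a non-inferiority purpose and a margin of 96, with only a two-sided difference test to decide.

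Every figure at SD 96.7 is conditional. It borrows the n of another outcome, from a source that the plan quotes in two ways (48-hour mean 3.39 with SE 0.37, and 3.8 with SE 0.36). It shows that neither stated power follows from the only available route; it does not establish the true power.

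A reader might conclude that the trial is too small. The documents do not support this. At SD 96.7, 36 per arm gives 98.6% at zero true difference and 85.1% at 26.6. Power below 80% at 26.6 would need an SD above about 104, and the SD is unknown.

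**What to change.** - Delete the conflicting power figure and the reference to 10.1.1.
- Confirm the AUC SD and n from the cited source and state both. Do not anchor on 96.7 until it is confirmed.
- Put one non-inferiority calculation in 6.1 and refer to it from 6.3: margin 96, one-sided alpha 0.025, the SD, and the assumed true difference. Zero is acceptable if stated.
- State the primary rule: conclude non-inferiority if the upper limit of the two-sided 95% CI for the AUC difference (PBA minus LB) is below 96.
- Keep 36 per arm and 80 in total, and restate whatever power results, at a true difference of zero and at 26.6.

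The cost is one check of a source, rewording of two sections and a changed primary decision rule, with no added patients. The change should be made before any outcome data are examined, including the interim analysis of the primary outcome in 6.6. The downside is that the restated power may be less favourable than 90%, and will be below 80% at 26.6 if the confirmed SD exceeds about 104.

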6.4 Accrual Rate

We plan on accruing 10 new patients per month until the goal of 80 total patients is reached.

Single Injection interscalene brachial plexus nerve block with adjuvants vs. Liposomal bupivacaine interscalene brachial plexus nerve block for total shoulder arthroplasty

6.5 Estimated Study Length

Estimated study length will be approximately 1 year.

6.6 Interim Analysis Plan

We will plan on performing an interim analysis for the primary outcome and secondary outcomes after there are at least 10 patients in each treatment group in order to detect the evidence of severe side effects in either group.

7.0 Adverse Event Reporting

Adverse event means any untoward medical occurrence associated with the use of a drug in humans, whether or not considered drug related.

Life-threatening adverse event or life-threatening suspected adverse reaction. An adverse event or suspected adverse reaction is considered "life-threatening" if, in the view of either the investigator or sponsor, its occurrence places the patient or subject at immediate risk of death. It does not include an adverse event or suspected adverse reaction that, had it occurred in a more severe form, might have caused death.

Serious adverse event or serious suspected adverse reaction. An adverse event or suspected adverse reaction is considered "serious" if, in the view of either the investigator or sponsor, it results in any of the following outcomes: Death, a life-threatening adverse event, inpatient hospitalization or prolongation of existing hospitalization, a persistent or significant incapacity or substantial disruption of the ability to conduct normal life functions, or a congenital anomaly/birth defect. Important medical events that may not result in death, be life-threatening, or require hospitalization may be considered serious when, based upon appropriate medical judgment, they may jeopardize the patient or subject and may require medical or surgical intervention to prevent one of the outcomes listed in this definition. Examples of such medical events include allergic bronchospasm requiring intensive treatment in an emergency room or at home, blood dyscrasias or convulsions that do not result in inpatient hospitalization, or the development of drug dependency or drug abuse.

Suspected adverse reaction means any adverse event for which there is a reasonable possibility that the drug caused the adverse event. For the purposes of IND safety reporting, "reasonable possibility" means there is evidence to suggest a causal relationship between the drug and the adverse event. Suspected adverse reaction implies a lesser degree of certainty about causality than adverse reaction, which means any adverse event caused by a drug.

Unexpected adverse event or unexpected suspected adverse reaction. An adverse event or suspected adverse reaction is considered "unexpected" if it is not listed in the investigator brochure or is not listed at the specificity or severity that has been observed; or, if an investigator brochure is not required or available, is not consistent with the risk information described in the general investigational plan or elsewhere in

Single Injection interscalene brachial plexus nerve block with adjuvants vs. Liposomal bupivacaine
interscalene brachial plexus nerve block for total shoulder arthroplasty

the current application, as amended. For example, under this definition, hepatic necrosis would be unexpected (by virtue of greater severity) if the investigator brochure referred only to elevated hepatic enzymes or hepatitis. Similarly, cerebral thromboembolism and cerebral vasculitis would be unexpected (by virtue of greater specificity) if the investigator brochure listed only cerebral vascular accidents. "Unexpected," as used in this definition, also refers to adverse events or suspected adverse reactions that are mentioned in the investigator brochure as occurring with a class of drugs or as anticipated from the pharmacological properties of the drug, but are not specifically mentioned as occurring with the particular drug under investigation.

The investigator will assess the relationship/causality of the AE to study drug after careful medical consideration on a case-by-case basis. General guidelines for determining the causality of an AE to the study drug are provided as follows:

Unrelated: A causal relationship between the study drug and the AE can be easily ruled out (e.g., based on the temporal sequence, absence of a reasonable pathophysiological mechanism, or direct evidence of actual cause).

Unlikely: A clinical event with a temporal relationship to study drug administration which makes a causal relationship improbable and in which other drugs, chemicals, or underlying disease provide a plausible explanation.

Possible: A clinical event with a reasonable time sequence to administration of the study drug but which could also be explained by a concurrent disease or other drugs or chemicals.

Probable: A clinical event with a reasonable time sequence to administration of the study drug unlikely to be attributed to a concurrent disease or other drugs or chemicals and which follows a clinically reasonable response on withdrawal (dechallenge).

Definite: The pharmacological properties of the study drug(s) or of the substance class, and the course of the AE after dechallenge and, if applicable, after rechallenge, and/or specific test indicate involvement of the study drug(s) in the occurrence/worsening of the AE, and no indication of other causes exists.

The investigator will assess the outcome of the AE after careful medical consideration, on a case-by-case basis. General guidelines are provided below:

Recovered/Resolved: The event resolved and the subject recovered from the AE.

Recovered/Resolved with Sequelae: The initial event resolved, but has a continuing abnormal condition as a result of the AE.

Not Recovered/Not Resolved: At the time of the last assessment, the event was ongoing, with an undetermined outcome.

Single Injection interscalene brachial plexus nerve block with adjuvants vs. Liposomal bupivacaine
interscalene brachial plexus nerve block for total shoulder arthroplasty

Recovering/Resolving: At the time of the last assessment, the event was decreasing in frequency, severity, etc., and a resolution was expected.

Fatal: The AE directly caused death.

Unknown: There was an inability to access the subject or the subject's records to determine the outcome (e.g., subject withdrew consent or was lost to follow-up).

The subject will receive adequate medical care by the medical provider for any adverse events related to the clinical trial. The investigator will provide any actions taken regarding the subject (e.g., treatment, diagnostic tests, laboratory tests, or therapy) for each reported AE. These include the following options:

- None.
- Medication.
- Non-pharmaceutical therapy. (The specific therapy used must be recorded in the data collection sheet)
- Discontinued from study.
- Other-document specific action taken

Serious and unexpected suspected adverse reaction: The investigator will report any suspected adverse reaction that is both serious and unexpected. The investigator will report an adverse event as a suspected adverse reaction only if there is evidence to suggest a causal relationship between the drug and the adverse event, such as if the study participation meets one of the following criteria:

- (A) A single occurrence of an event that is uncommon and known to be strongly associated with drug exposure;
- (B) One or more occurrences of an event that is not commonly associated with drug exposure, but is otherwise uncommon in the population exposed to the drug;
- (C) An aggregate analysis of specific events observed in a clinical trial (such as known consequences of the underlying disease or condition under investigation or other events that commonly occur in the study population independent of drug therapy) that indicates those events occur more frequently in the drug treatment group than in a concurrent or historical control group.

In case a cardiac or neurological AE of special interest (AESI) or serious AE (SAE) occurs during the study, if the investigator considers that the event may be related to study treatment or suggests the possible occurrence of local anesthetic systemic toxicity (LAST; with or without the need for treatment [e.g., intralipids]), or if a plausible etiology for the event cannot be found, vital signs, and clinical laboratory tests will be performed per institutional standard of care of such occurrence. Cardiac AESIs include chest pain, abnormal/irregular heart rate, and shortness of breath requiring intervention.

Single Injection interscalene brachial plexus nerve block with adjuvants vs. Liposomal bupivacaine interscalene brachial plexus nerve block for total shoulder arthroplasty

Neurologic AESIs include seizure, altered mental status/ altered sensorium, tinnitus, visual disturbance, and severe dizziness.

This study involves a single administration of the study drug for the analgesic block; therefore, subjects should not be withdrawn from the ongoing study assessments as long as they are willing and able to continue with the follow-up schedule according to the protocol in order to obtain analgesic and safety data. Any subject exhibiting undesirable AESIs will receive appropriate treatment at the discretion of the investigator.

Subjects will be monitored for the occurrence of all potential adverse events by research personnel. This clinical research study will be paused after one death where a clear alternate cause is not readily apparent. The study will be paused after 2 non-fatal SAEs where a clear alternate cause is not readily apparent; the study will be paused after 3 moderate or severe adverse events of special interest. The adverse event(s) will be assessed by all investigators for causality and relationship prior to the study enrollment being resumed. Assessment of adverse event severity will be assessed and graded as per the definitions noted in Appendix I.

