APPENDIX I: ADVERSE EVENT GRADING SCALES

| LOCAL REACTION TO INJECTABLE PRODUCT | Mild (Grade 1) | Moderate (Grade 2) | Severe (Grade 3) | Potential life threatening (Grade 4) |
|--------------------------------------|----------------------------------------------------------|----------------------------------------------------------------------------------|--------------------------------------------------------------|--------------------------------------------------------|
| Pain | Does not interfere with activity | Repeated use of non-narcotic pain reliever >24 hours or interferes with activity | Any use of narcotic pain reliever or prevents daily activity | Emergency room visit or hospitalization |
| Tenderness | Mild discomfort to touch | Discomfort with movement | Significant discomfort at rest | Emergency room visit or hospitalization |
| Erythema/Redness | 2.5-5 cm | 5.1-10 cm | >10 cm | Necrosis or exfoliative dermatitis |
| Induration/Swelling | 2.5-5 cm and does not interfere with activity | 5.1-10 cm or interferes with activity | >10 cm or prevents daily activity | necrosis |
| <hr/> | | | | |
| VITAL SIGNS | Mild (Grade 1) | Moderate (Grade 2) | Severe (Grade 3) | Potentially Life threatening (Grade 4) |
| Fever-*F | 100.4-101.1 | 101.2-102.0 | 102.1-104 | >104 |
| Tachycardia | 101-115 | 116-130 | >130 | ER visit or hospitalization for arrhythmia |
| Bradycardia | 50-54 | 45-49 | <45 | ER visit or hospitalization for arrhythmia |
| Hypertension-systolic | 141-150 | 151-155 | >155 | ER visit or hospitalization for malignant hypertension |
| Hypertension-diastolic | 91-95 | 96-100 | >100 | ER visit or hospitalization for malignant hypertension |
| Hypotension | 85-89 | 80-84 | <80 | ER visit or hospitalization for hypotensive shock |
| Respiratory rate | 17-20 | 21-25 | >25 | Intubation |
| <hr/> | | | | |
| SYSTEMIC (GENERAL) | Mild (Grade 1) | Moderate (Grade 2) | Severe (Grade 3) | Potentially Life threatening (Grade 4) |
| Nausea/vomiting | No interference with activity or 1 – 2 episodes/24 hours | Some interference with activity or > 2 episodes/24 hours | Prevents daily activity, requires outpatient IV hydration | ER visit or hospitalization for hypotensive shock |
| Diarrhea | 2 – 3 loose stools | 4 – 5 stools | 6 or more watery stools or requires IV hydration | ER visit or hospitalization |

Single Injection interscalene brachial plexus nerve block with adjuvants vs. Liposomal bupivacaine

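### Read literally, the AESI pause rule counts Grades 2 and 3 but not Grade 4, and the two-SAE rule only partly covers the gap

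*Combined protocol and SAP*

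**What the plan says.** Section 7.0 sets three pause triggers. One is a single death without a clear alternate cause. The second reads: "The study will be paused after 2 non-fatal SAEs where a clear alternate cause is not readily apparent". The third reads: "the study will be paused after 3 moderate or severe adverse events of special interest". After a pause, all investigators assess causality before enrollment resumes.

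The same paragraph ties the severity words to a scale: "Assessment of adverse event severity will be assessed and graded as per the definitions noted in Appendix I". Appendix I has four levels: mild (Grade 1), moderate (Grade 2), severe (Grade 3), and a further column headed "Potentially Life threatening (Grade 4").

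For tachycardia and bradycardia the Grade 4 entry is "ER visit or hospitalization for arrhythmia". The general row for clinical adverse events, which serves AESIs without a row of their own, also makes an ER visit or hospitalization Grade 4.

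Section 7.0 defines seriousness separately. The listed outcomes begin with "Death, a life-threatening adverse event, inpatient hospitalization or prolongation of existing hospitalization". The life-threatening criterion requires immediate risk of death, and the text adds: "It does not include an adverse event or suspected adverse reaction that, had it occurred in a more severe form, might have caused death". There is also a route by judgment: "Important medical events that may not result in death, be life-threatening, or require hospitalization may be considered serious when, based upon appropriate medical judgment". The examples given for that route include convulsions without admission.

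**The concern.** The AESI trigger uses two words that the protocol itself assigns to the two middle grades of a four-grade scale. Taken at face value, it excludes mild events, as intended, but also excludes the worst ones. A pause rule should never become harder to trigger when an event gets worse.

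What is at stake is the mandatory pause and joint causality review. The pause triggers in Section 7.0 are the only numerical safety thresholds in the plan. The interim look in Section 6.6 is meant to detect severe side effects but states no threshold. Patients are followed to 48 hours, partly at home by phone, so an AESI that leads to an ER visit after discharge is a realistic way to reach Grade 4.

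**Working it through.** The plan gives no operating characteristic for this rule, so there is no figure to reproduce. The check sets the definitions side by side and then counts.

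**Step 1: is every Grade 4 AESI an SAE?** No.

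| Feature | Grade 4 (Appendix I) | SAE (Section 7.0) |
|---|---|---|
| Hospital contact | ER visit is enough (arrhythmia and general rows) | Inpatient stay or its prolongation |
| Threat to life | Potential | Immediate risk of death only |
| ER visit, no admission | Grade 4 | Only by medical judgment; convulsions are a named example |

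Seizure is a listed AESI, so for that event the text points toward SAE status even without admission. For the other AESIs, an ER-only event depends on judgment.

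**Step 2: the rule as written.** Let A be the number of AESIs of Grade 2 or 3, and S the number of non-fatal SAEs without a clear alternate cause. Leaving deaths aside, the study pauses if A ≥ 3 or S ≥ 2. The two counts are not pooled. The AESI rule has no alternate-cause condition; the SAE rule does.

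**Step 3: four mixes of three AESIs.** Assumptions: the Grade 2–3 events are not SAEs, and there is no other SAE and no death. S then comes only from Grade 4 events.

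| Grade 2–3 events | Grade 4 events | A | Possible S | Pause as written? |
|---|---|---|---|---|
| 3 | 0 | 3 | 0 | Yes (A = 3) |
| 2 | 1 | 2 | 0 or 1 | No, for either value of S |
| 1 | 2 | 1 | 0, 1 or 2 | Only if S = 2 |
| 0 | 3 | 0 | 0, 1, 2 or 3 | Only if S ≥ 2 |

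The second row is the inversion. Making one of three Grade 2 events worse lowers A from 3 to 2 and raises S to at most 1, so neither threshold is met.

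The alternate-cause condition matters in the last row. Three Grade 4 SAEs that each have a clear alternate cause give A = 0 and S = 0, so no pause. Three Grade 2 AESIs with equally clear alternate causes give A = 3, so a pause.

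**Step 4: relaxing the assumption.** A Grade 2–3 event can itself be serious, for example by prolonging a hospital stay. If one of the two Grade 2–3 events in the second row is an SAE without a clear alternate cause, and the Grade 4 event is too, then S = 1 + 1 = 2 and the study pauses. The contrast in Step 3 therefore holds only under its stated assumption.

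**Step 5: the reworded rule.** If A counts all AESIs of Grade 2 or higher, then A = 3 in all four rows and every row pauses.

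**The case against.** The strongest reply is that nobody would apply the rule this way. In a pause rule, 'moderate or severe' naturally means 'not mild'. Appendix I does not say that an event meeting a Grade 4 criterion stops meeting the severe one. On the general row, Grade 4 is set by place of care, so many such events would also fit the severe description. A sensible investigator would count them. This is persuasive about intent and is the reason the point is minor. It does not close the gap: the plan defines severe as Grade 3 and nowhere says that Grade 4 counts as well.

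A second reply is that most Grade 4 AESIs would be SAEs, and the SAE rule then acts sooner, at two events rather than three. That is right for SAEs without a clear alternate cause. Events during the hospital stay that prolong it are serious by definition, and convulsions are named as an example. It does not help with a single Grade 4 event, with explained SAEs, or with ER-only events not judged serious.

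A third reply is that other oversight remains. Perioperative adverse safety events go to the PI, who records them and contacts the patient. SAEs are reviewed by the PI and reported to the IRB within 48 hours (Section 5.5), and Section 6.6 adds an interim look once each group has at least 10 patients. All of this stands. A Grade 4 event would be noticed; what may be missed is the mandatory pause.

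A reader might infer that the plan lets life-threatening events accumulate without ever stopping. The documents do not support that: two non-fatal SAEs without a clear alternate cause pause the study whatever their grade, as does one death without such a cause.

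**Conclusion.** The point holds as a wording defect: minor, but wrong as written. Followed literally, the AESI trigger omits Grade 4, and the two-SAE rule covers the omission only in part. The clearest consequence is that three Grade 2 AESIs pause the study, while two Grade 2 AESIs plus one Grade 4 AESI do not. This assumes that the Grade 2 events are not SAEs and that there is no other SAE or death.

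The table lists event patterns, not probabilities. The documents give no AESI rates, so a reader should not infer how often a pause would be missed. Nor should the omission be read as a deliberate choice to exempt the worst events; it is probably unintended. It affects safety oversight only and leaves the primary analysis and sample size untouched.

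**What to change.** In the third pause trigger of Section 7.0, replace 'moderate or severe' with **Grade 2 or higher per Appendix I**, and leave the death and SAE triggers as they are. A Grade 4 AESI that is also an SAE without a clear alternate cause would then count under both rules, which is harmless.

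The cost is a one-phrase amendment with no new procedures. The only downside is possibly an extra temporary pause for causality review.
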